8.4 Withdrawal of individual research participants

Participants can leave the study at any time for any reason without any consequences if they wish to do so. The investigator can decide to withdraw a participant from the study for urgent medical reasons.

8.5 Replacement of individual research participants after withdrawal

Participants will not be replaced after withdrawal.

8.6 Follow-up of research participants withdrawn from treatment

Patients withdrawn from the study will get the usual care according to their hospital. This care is hospital-dependent. In case data are already collected, these data will be used in the study unless the patient also revokes the consent to use the collected data. Patients will be asked whether data may still be collected from the EPD and LROI register after withdrawal.

8.7 Premature termination of the study

As both the COD and RFU are part of standard care, we do not expect premature termination of the study. Only in case the study will jeopardize participant's health or safety, the study will be prematurely terminated. In case of premature termination of the study, participants will be followed up according to the standard care according to their hospital. Participants are not at additional risk when the study is terminated prematurely.

9. SAFETY REPORTING

9.1 Temporary halt for reasons of research participant safety

In accordance to section 10, subsection 4, of the WMO, the sponsor will suspend the study if there is sufficient ground that continuation of the study will jeopardise participant health or safety. The sponsor will notify the review committee without undue delay of a temporary halt including the reason for such an action. The study will be suspended pending a further positive decision by the review committee. The investigator will take care that all participants are kept informed.

9.2 AEs, SAEs

9.2.1 Adverse events (AEs)

Adverse events are defined as any undesirable experience occurring to a participant during the study, whether or not considered related to the experimental intervention (RFU or COD). In this study, complications, surgical interventions, and healthcare use are systematically collected as part of the study outcomes and are therefore already recorded. As such, these do not need to be reported separately as adverse events. Only events that can be directly linked to the presence or absence of the clinical visit and X-ray 1 year after surgery should be reported as adverse events.

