12. ADMINISTRATIVE ASPECTS, MONITORING AND PUBLICATION	31
12.1Handling and storage of data and documents	31

12.2	Monitoring and Quality Assurance.....	31
12.3	Amendments.....	32
12.4	Annual progress report.....	32
12.5	Temporary halt and (prematurely) end of study report.....	32
12.6	Public disclosure and publication policy	32
13.	STRUCTURED RISK ANALYSIS.....	33
14.	REFERENCES	34

LIST OF ABBREVIATIONS AND RELEVANT DEFINITIONS

AE	Adverse Event
CCMO	Central Committee on Research Involving Human Subjects; in Dutch: Centrale Commissie Mensgebonden Onderzoek
COD	Check-up on demand
EPD	Electronic patient record system
FU	Follow-up
GCP	Good Clinical Practice
GDPR	General Data Protection Regulation; in Dutch: Algemene Verordening Gegevensbescherming (AVG)
HCP	Health care professional
IC	Informed Consent
LROI	Dutch Arthroplasty Register
METC	Medical research ethics committee (MREC); in Dutch: medisch-ethische toetsingscommissie (METC)
Review committee	Medical research ethics committee (MREC) or CCMO
RFU	Routine follow-up
(S)AE	(Serious) Adverse Event
Sponsor	The sponsor is the party that commissions the organisation or performance of the research, for example a pharmaceutical company, academic hospital, scientific organisation or investigator. A party that provides funding for a study but does not commission it is not regarded as the sponsor, but referred to as a subsidising party.
THA	Total hip arthroplasty
TKA	Total knee arthroplasty
UAVG	Dutch Act on Implementation of the General Data Protection Regulation; in Dutch: Uitvoeringswet AVG
WMO	Medical Research Involving Human Subjects Act; in Dutch: Wet Medisch-wetenschappelijk Onderzoek met Mensen

SUMMARY

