3. STUDY DESIGN

During the grant application process, all relevant stakeholders were involved in setting up this study protocol during a co-creation process. The co-creation team consisted of representatives from patient associations, healthcare insurers, the knowledge institute of the federation of medical specialists, the national healthcare institute, methodological and statistical expertise, the Netherlands Orthopaedic Association (NOV), the ZE&GG program for appropriate healthcare, and the project team. ZE&GG organized meetings to discuss crucial points with the stakeholders, which resulted in a well-considered research protocol approved by all involved stakeholders. The NOV signed a declaration of support and commits to implementation of the results.

In this study a randomized controlled trial with 3 arms will be performed. Patients will be randomized 1:1:1 in the following groups:

[figure not shown]
1. RFU: routine follow-up at 10 years after THA or TKA (control)
2. Active COD: No RFU at 10 years. Patients will be informed about the study and complete questionnaires. Check-ups are scheduled only on demand by the patient or health care professional (HCP) (intervention)
3. Passive COD: No RFU at 10 years. Patients will not be informed about the study to avoid any trigger to contact a HCP and will not complete questionnaires (intervention)

Patients will be followed for 1 year after RFU or COD (11 years after surgery). Informing the patients about the study and letting them complete questionnaires might result in trigger bias to contact a HCP. Therefore, patients in the intervention group will be divided into two groups: 1) one group will be informed about the study and complete questionnaires (active COD), 2) the other group will not be contacted and informed about the study to avoid trigger bias (passive COD). Of the latest group, only data from the LROI and EPD will be used. The control group will receive RFU at 10 years after THA or TKA and will complete questionnaires. Both groups completing questionnaires (active COD and RFU group) will be actively asked to participate in the study and to complete questionnaires and therefore will be randomized after informed consent.

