8.3 Study procedures

This study will be conducted in 10 Dutch hospitals across the Netherlands. Patients will be recruited using the LROI register and EPD. After inclusion, baseline characteristics will be obtained from the EPD and LROI register. Information on patient background will be collected to explore potential differences in follow-up needs, including among patients with different ethnic backgrounds. Previous research shows that people with a migrant background visit specialists and hospitals less often than native Dutch patients with similar health and SES [21]. Acknowledging the sensitivity of this topic, a 'prefer not to say' option is provided.

Patients will be scheduled for a clinical visit or not depending on the randomization group. The clinical visit contains of a check by the orthopaedic surgeon or orthopaedic resident and an X-ray. Additionally, a physical examination can be performed in case of concerns.

Information about the clinical visit will be collected. The patient or the HCP can also schedule a clinical visit in case of concerns, pain or symptoms. Information about these visits will also be collected.

Patients randomized to the active COD or RFU group will be asked to complete the questionnaires online or on paper. Completion time will be around 10-25 minutes. Table 1 depicts the data collection and assessments at baseline and during follow-up appointments.

Study data will be collected onto an electronic case report form (eCRF) in Castor EDC. The primary outcome will be measured at 11 years after surgery, i.e. 1 year after RFU or COD at 10 years. EQ-5D-5L and costs will be measured at 10 years after surgery (baseline), and at 3, 6, and 12 months after baseline in the RFU and active COD group. The other outcomes will be measured only at 10 years (baseline) and 11 years after surgery (end point).

Table 1: Overview of data collection and assessments.

	Baseline (10 years after surgery) (+/- 30 days)	In case of check-up on demand (10-11 years after surgery)	3 months (+/- 30 days)	6 months (+/- 30 days)	12 months (11 years after surgery) (+/- 30 days)
Clinical visit	X*	X			
Physical examination [#]	X	X			
X-ray	X*	X [#]			
Healthcare consumption	X	X	X	X	X
Questionnaires:**					
PROMIS	X				X
EQ-5D-5L	X		X	X	X
NPRS	X				X
NSRS	X				X
Costs	X		X	X	X

* Only RFU group

[#] In case of concerns

** Not for passive COD group

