9.2.2 Serious adverse events (SAEs)

A serious adverse event is any untoward medical occurrence or effect that

- results in death;
- is life threatening (at the time of the event);
- requires hospitalisation or prolongation of existing inpatients' hospitalisation;
- results in persistent or significant disability or incapacity;
- is a congenital anomaly or birth defect; or
- any other important medical event that did not result in any of the outcomes listed above due to medical or surgical intervention but could have been based upon appropriate judgement by the investigator.

Only events that are related to the study procedures (RFU or COD) will be considered as serious adverse events. An elective hospital admission will not be considered as a serious adverse event.

Due to the intervention (COD or RFU) hardly any SAEs are to be expected. This means all (S)AEs related to participation in this study protocol, meaning from COD

and RFU, will not be reported to the METC, as no patient benefit is expected from this.

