12.4 Annual progress report

The sponsor/investigator will submit a summary of the progress of the trial to the review committee once a year. Information will be provided on the date of inclusion of the first participant, numbers of participants included and numbers of participants that have completed the trial, serious adverse events, other problems, and amendments.

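### The adverse event rule in section 9.2.1 names a visit 1 year after surgery, but the randomised visit is at 10 years; a lesser point is that 9.2.2 and 12.4 need aligning on SAEs

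*Protocol*

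**What the plan says.** **Adverse events.** Protocol section 9.2.1 first defines an adverse event broadly, as any undesirable experience during the study, related to RFU or COD or not. It then exempts complications, surgical interventions and healthcare use from separate reporting, because they are collected as outcomes. Its last sentence sets what remains to be reported: "Only events that can be directly linked to the presence or absence of the clinical visit and X-ray 1 year after surgery".

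**The visit under study.** Section 3 describes the control arm as "routine follow-up at 10 years after THA or TKA (control". Section 4.2 admits patients operated on about 10 years earlier. Section 8.3 states: "The primary outcome will be measured at 11 years after surgery, i.e. 1 year after RFU or COD at 10 years".

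**Serious adverse events.** Section 9.2.2 narrows the class: "Only events that are related to the study procedures (RFU or COD) will be considered as serious adverse events". It then says of all (S)AEs arising from COD "and RFU, will not be reported to the METC, as no patient benefit is expected from this".

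**Annual report.** Section 12.4 states: "The sponsor/investigator will submit a summary of the progress of the trial to the review committee once a year". The listed content includes "numbers of participants that have completed the trial, serious adverse events, other problems, and amendments". The list of abbreviations defines the review committee as "Medical research ethics committee (MREC) or CCMO" and gives METC as the Dutch term for the MREC.

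**The concern.** The last sentence of 9.2.1 is an operative rule. It tells a site which events to report as adverse events, and so which events fall under the follow-up duty in 9.3. It should therefore name the visit that patients are randomised to have or to skip. It names a different one.

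The second question is what the review committee receives. Section 1 gives missed complications as the main worry about dropping the visit, and section 10.5 plans no interim analysis. The annual report is the only scheduled route by which the committee sees SAEs while the trial runs. The protocol should be clear on whether related SAEs appear in it.

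**Working it through.** The plan gives no figure on this point to reproduce. The check sets the sections side by side, with simple arithmetic on the timing.

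**Step 1: does the visit named in 9.2.1 exist in this trial?**

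| Source (Protocol) | Time after surgery |
|---|---|
| 9.2.1, AE reporting rule | 1 year |
| 3, RFU arm | 10 years |
| 4.2, eligibility | about 10 years |
| 8.3, Table 1, baseline | 10 years |
| 8.3, Table 1, end point | 11 years |

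- Distance from the named visit to study baseline: 10 − 1 = 9 years.
- Scheduled time points in Table 1: baseline and 3, 6 and 12 months, which are years 10, 10.25, 10.5 and 11.
- Each has a window of 30 days either side, and 30/365 = 0.08 years. The earliest window opens at 10 − 0.08 = 9.92 years and the latest closes at 11 + 0.08 = 11.08 years.
- None of the four windows contains year 1.

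**Step 2: could the phrase mean 1 year after RFU or COD?** No. The sentence counts from surgery. In Table 1 the clinical visit and X-ray are marked only at baseline (RFU group) and for a check-up on demand, with no mark at 12 months. So no visit or X-ray is planned at year 11 whose presence or absence could cause an event. A visit at 1 year after surgery appears elsewhere only as guideline background, in the Summary and section 1.

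**Step 3: does the slip reach the SAE rule?** No. Section 9.2.2 ties SAEs to the study procedures, RFU or COD, and names no year.

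**Step 4: do 9.2.2 and 12.4 agree?**

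- SAEs recognised by 9.2.2: only those related to RFU or COD.
- (S)AEs that 9.2.2 keeps from the METC: all those arising from RFU or COD.
- These cover the same SAEs. If 9.2.2 bars every form of reporting, nothing is left for the SAE item in 12.4.
- The recipient appears to be the same body. The review committee is the MREC (METC) or the CCMO, and section 11.4 has the METC granting the insurance dispensation.
- Section 9.2.2 does not limit its statement to individual or expedited reports. Section 12.4 describes a yearly summary. The two can be reconciled only by adding a limit that 9.2.2 does not state.

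**The case against.** **The intended visit is obvious.** Section 9.2.1 speaks of events during the study and names the intervention as RFU or COD. The study starts at year 10, and nobody is randomised to a visit at year 1, so a sensible site would read 10 years. This stands, and it limits the consequence. It does not make the sentence right: an operative safety criterion should not depend on the reader correcting it.

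**Safety data would be lost.** A reader might infer this, but the protocol does not support it. Complications, surgical interventions and healthcare use are collected as outcomes whatever 9.2.1 says, and section 8.3 records the reason for each clinical visit and the consequences of any findings. No specific event that would go unrecorded has been identified.

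**Sections 9.2.2 and 12.4 flatly contradict each other, and the committee is kept uninformed.** This is also tempting and also too strong. Section 9.2.2 sits under safety reporting and can reasonably be read as waiving reports of individual events. Section 12.4 concerns an aggregate yearly summary, which is a different channel. Section 9.1 separately requires the committee to be told without undue delay if the study is suspended for participant safety. What remains is an ambiguity, because 9.2.2 covers all related (S)AEs without qualification.

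**The fix chooses for the sponsor.** Removing SAEs from 12.4 would also make the two sections consistent, and the protocol does not say which is meant. That is fair. The alternative is named under the fix.

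**Conclusion.** Section 9.2.1 is wrong as written and should be corrected. It ties adverse event reporting to a visit 9 years before baseline that is not part of the trial, when the only randomised visit and X-ray are at 10 years. Read literally, it captures no adverse event caused by the allocated strategy.

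The relation between 9.2.2 and 12.4 is a lesser matter. It is an ambiguity to resolve and does not show a second rule to be wrong. Two assumptions underlie it: that the METC is the review committee for this trial, as section 11.4 indicates, and that the likely intent of 9.2.2 is to waive individual reporting only.

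The practical effect of both is limited. The clinically important events are collected as outcomes, the SAE definition names no year, and no sample size, power or analysis changes. Neither point is a flaw in the trial's design.

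**What to change.** 1. In the last sentence of 9.2.1, change the time point to *10 years after surgery*. Nothing else in the sentence needs to change.
2. In the last sentence of 9.2.2, limit the waiver, for example: *(S)AEs arising from COD or RFU are not reported individually to the METC; serious adverse events are listed in the annual progress report (section 12.4).*

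If the sponsor intends no SAE reporting to the committee at all, 12.4 would have to change instead. Keeping the annual listing is the safer choice, since it is the only scheduled report of SAEs to the committee during the trial.

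The cost is two sentences of protocol wording. No new data, visits, causality assessments or analyses are needed.

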9.2.2 Serious adverse events (SAEs)

A serious adverse event is any untoward medical occurrence or effect that

- results in death;
- is life threatening (at the time of the event);
- requires hospitalisation or prolongation of existing inpatients' hospitalisation;
- results in persistent or significant disability or incapacity;
- is a congenital anomaly or birth defect; or
- any other important medical event that did not result in any of the outcomes listed above due to medical or surgical intervention but could have been based upon appropriate judgement by the investigator.

Only events that are related to the study procedures (RFU or COD) will be considered as serious adverse events. An elective hospital admission will not be considered as a serious adverse event.

Due to the intervention (COD or RFU) hardly any SAEs are to be expected. This means all (S)AEs related to participation in this study protocol, meaning from COD

and RFU, will not be reported to the METC, as no patient benefit is expected from this.

9.3 Follow-up of adverse events

All AEs will be followed until they have abated, or until a stable situation has been reached. Depending on the event, follow-up may require additional tests or medical procedures as indicated, and/or referral to the general physician or a medical specialist.

10. STATISTICAL ANALYSIS

All analyses will be performed separately for THA and TKA and will be performed using IBM SPSS statistics (SPSS software version 28.0) or R. Categorical data will be presented as numbers and percentages. Continuous variables will be presented by mean and standard deviation in case of a normal distribution. In case of non-normality, median and interquartile range will be given.

Mixed models are used to deal with missing data; when necessary and possible we will perform multiple imputation.

10.1 Primary study parameter(s)

The total number of complications at 1 year follow-up (11 years after surgery) and process evaluation expressed by the health care consumption, like the number of clinical visits and X-rays, will be presented by median and interquartile range. For the primary aim, the number of complications will be compared between 2 groups, namely the RFU and active COD, using generalized linear mixed models (GLMM), with a Poisson distribution. A random intercept for centre will be included in the model to account for clustering of patients within centres and a main effect for group is added to determine treatment effect. We will also determine adjusted intervention effects, by accounting for relevant baseline characteristics such as age, gender, BMI, ASA-score, ethnicity, employment status, home-hospital distance and educational level.

The type of complications at 1 year follow-up (11 years after surgery) will be presented categorically by numbers and percentages. The type of complications will be compared between 2 groups (RFU vs. active COD) using GLMM with a logistic regression approach, including a main effect for group, a random intercept for centre and adjusting for baseline characteristics such as age, gender, BMI, ASA-score, ethnicity, employment status, home-hospital distance and educational level.

Process evaluation outcomes will also be expressed dichotomously (i.e. clinical visit: yes/no, X-ray: yes/no etc.) and analysed using logistic GLMM.

The primary outcomes are based on intention-to-treat analyses.

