4.4 Sample size calculation

We carefully determined the required number of patients to ensure reliable outcome estimates in collaboration with co-creating stakeholders and by consulting orthopaedic surgeons using an online survey on what constitutes convincing evidence. The agreed sample size is 250 patients per group. Therefore, we plan to randomize 250 patients per study group resulting in a total of 750 THA and 750 TKA patients.

To provide a rough indication of the statistical power, we used the online power calculator tool available on Sealed Envelope [20]. The sample size calculation is based on the comparison of RFU vs. active COD as the primary analysis. For this calculation, we assumed that the actual complication rate in both groups is 10%. With the agreed number, it is possible to detect a clinical relevant difference of 10% in complications between the two groups. If there is truly no difference between active COD and RFU, 190 patients per group are needed to be 80% sure that the limits of a two-sided 95% confidence interval will exclude a difference between active COD and RFU of more than 10%. Anticipating 20-25% loss to follow up, we plan to randomize 250 patients.

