10.2 Secondary study parameter(s)

For the secondary analysis, the aforementioned GLMM analyses on number and type of complications and clinical visits will be repeated comparing the 3 groups, namely the RFU, active COD and passive COD.

Secondary patient-reported outcomes, namely PROMIS physical function, NPRS, NSRS and EQ-5D-5L, will be presented as mean with standard deviation in case of normality or median and interquartile range otherwise. These parameters will be analysed using linear mixed models, with repeated measures clustered within participants and participants within

hospitals (random intercepts). Intervention group (RFU vs. active COD vs. passive COD), baseline score, and time (3, 6, 12 months) are included as fixed effects, to determine the crude effect of the intervention. To correct for possible confounders, baseline variables will be added to the model as fixed effects.

The total number of surgical interventions at 1 year follow-up (11 years after surgery) will be presented by median and interquartile range. The number of complications will be compared between 3 groups, namely the RFU, active COD and passive COD, using GLMM, with a Poisson distribution. A random intercept for the centre will be included in the model to account for clustering within centres. GLMM will also be used to correct for and to investigate the effect of possible confounders..

The type of surgical interventions at 1 year follow-up (11 years after surgery) will be presented categorically by numbers and percentages. The type of surgical interventions will be compared between 3 groups using GLMM with logistic regression, adjusting for possible confounders and incorporating centre as a random intercept.

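### Median and interquartile range for the number of complications and surgical interventions will usually read 0 (0-0) in both compared arms, even at the full 10-point margin, and no planned output gives the proportion of patients with any complication

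*Protocol*

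**What the plan says.** Section 10.1 names the variable, "The total number of complications at 1 year follow-up (11 years after surgery) and process evaluation expressed by the health care consumption", and then sets its summary: "like the number of clinical visits and X-rays, will be presented by median and interquartile range". The comparison of RFU with active COD is made separately, by a Poisson generalised linear mixed model with a random intercept for centre.

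Section 10.1 adds two other outputs. Type of complication is tabulated by number and percentage and compared by logistic mixed model. The process outcomes (visits, X-rays) are also analysed as yes/no. The count of complications gets no yes/no version.

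Section 10.2 repeats the rule for surgery: "The total number of surgical interventions at 1 year follow-up (11 years after surgery) will be presented by median and interquartile range". Type of surgery is again given by number and percentage.

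The sample size in section 4.4 is on the proportion scale. For RFU versus active COD it states "we assumed that the actual complication rate in both groups is 10" per cent, and that "it is possible to detect a clinical relevant difference of 10% in complications between the two groups".

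**The concern.** A median with quartiles describes a count well only when a fair share of patients have a non-zero value. Section 4.4 expects about nine patients in ten to have no complication, so the three order statistics are likely to be zero in both compared arms.

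The margin is an absolute difference in the percentage of patients with a complication. The stated summary cannot show that percentage at the rates the trial is planned around. The Poisson model reports a ratio, which does not by itself place the result against a margin in percentage points. A reader deciding whether routine follow-up can be dropped needs the absolute rate per arm, and the plan does not promise it.

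**Working it through.** **Inputs (Protocol section 4.4).** Complication rate p = 0.10 in RFU and active COD; margin d = 0.10; two-sided 95% interval; 80% power; 190 evaluable and 250 randomised per group. Analyses are separate for THA and TKA (section 10), so these are the arm sizes within each procedure.

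**1. Reproduce the plan's sample size.** The section states "190 patients per group are needed to be 80% sure" of ruling out, in either direction, a gap larger than the margin when the arms do not truly differ. The equivalence formula for two proportions gives

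n = 2p(1 − p)(z0.975 + z0.90)² / d² = 2 × 0.10 × 0.90 × (1.960 + 1.282)² / 0.10² = 189.1, so 190 per group.

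For attrition, 190/0.80 = 238 and 190/0.75 = 254 (rounded up). The planned 250 lies inside this range. The figure is reproduced, and it treats 10% as the proportion of patients with a complication.

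**2. Expected quartiles.** The upper quartile is zero whenever at least about 75% of patients have a zero count.

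| True rate | P(count = 0), at most one event each | P(count = 0), Poisson count | Q1, median, Q3 |
|---|---|---|---|
| 0.10 | 0.90 | exp(−0.10) = 0.905 | 0, 0, 0 |
| 0.20 | 0.80 | exp(−0.20) = 0.819 | 0, 0, 0 |

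The upper quartile leaves zero only when more than about 25% of patients have an event. For a Poisson count this means a mean above −ln(0.75) = 0.288.

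**3. Chance that a sample upper quartile exceeds zero.** This needs at least 48 of 190, or 63 of 250, patients with an event. The probability is a binomial upper tail with success probability r (at most one event each) or 1 − exp(−r) (Poisson).

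| True rate r | n | At most one event each | Poisson count |
|---|---|---|---|
| 0.10 | 190 | 1.3 × 10⁻⁹ | 2.6 × 10⁻¹⁰ |
| 0.10 | 250 | 4.7 × 10⁻¹² | 5.4 × 10⁻¹³ |
| 0.20 | 190 | 4.5% | 0.9% |
| 0.20 | 250 | 2.6% | 0.3% |

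A simulation of 20,000 samples per setting agrees: at r = 0.20 with at most one event each, 4.7% (n = 190) and 2.6% (n = 250). The sample median was zero in every simulated sample with at most one event each.

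So 0 (0-0) appears in about 95% (n = 190) to 97% (n = 250) of samples at a true 20%, and in over 99% under a Poisson count. At 10% it is near certain, so the probability that both arms show it when they differ by the full margin is also about 95% to 97%.

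**4. What other summaries would show at the same inputs.** At 10% versus 20%: 25 versus 50 of 250 patients (19 versus 38 of 190), or mean counts of 0.10 versus 0.20.

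**5. Surgical interventions.** The protocol gives no assumed rate. Section 8.1.1 counts as complications those problems that lead to extra follow-up, referral or intervention, so I assume surgery is no more frequent than complications. On that assumption the result carries over.

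**The case against.** The strongest reply is that this is a matter of description only. The medians enter no estimate, test or interval. The Poisson model compares the arms whatever the medians show, so bias, power and the primary comparison are untouched. That stands.

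A reader might infer that the arms would look identical whatever happened. The documents do not support this. The model's group effect is reported, and so are complications by type, which at 10% versus 20% would visibly differ. The summary also becomes informative above about 25%. The complication definition is broad, so a higher true rate is possible, although it would contradict the planning assumption.

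A reader might also infer that total events per arm cannot be recovered. If every complication is classified and counted by type, the type counts add up to the total. If patients are counted within type, the sum is only approximate. Neither gives the number of patients with any complication, because one patient can appear under several types.

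Two further limits are fair. The 10% is assumed for RFU and active COD, not for passive COD; for that arm the result depends on its rate being below about 25%. And 0 (0-0) at a true 20% is the expected result, not a certain one.

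Table layout is often left to a statistical analysis plan. Here, though, the protocol itself states the summary, and the stated choice suits these counts badly. Finally, a risk difference is an added comparison rather than a description, and it has to deal with centre. That is a real, though small, cost.

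**Conclusion.** The point holds as a reporting weakness and a cheap improvement. At the protocol's own 10% rate, and usually at 20%, the stated summary of the primary clinical endpoint will be 0 (0-0), so it would usually hide a difference as large as the one the trial is sized to exclude. The gap that remains after the other outputs are counted is specific: no planned output gives the proportion of patients with any complication, or an absolute between-arm difference, on the scale of the 10-point margin.

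It would be wrong to conclude that the primary analysis is invalid or that the arms could not be told apart in the report. The size rests on the 10% assumption of section 4.4 and on arms of 190 to 250. For surgery it also rests on the assumption that surgery is no more frequent than complications.

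**What to change.** In sections 10.1 and 10.2, for complications and surgical interventions, replace median and interquartile range with three figures per arm:

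- the number and percentage of patients with at least one event;
- the total number of events;
- the mean number of events per patient.

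For complications in RFU versus active COD, add the risk difference with its 95% confidence interval, accounting for centre and given separately for THA and TKA, so that the result can be read against the 10-point margin. The Poisson model can stay as it is. Median and interquartile range may stay for visits and X-rays, which already have a yes/no version.

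The cost is a change of wording in two sections and a small amount of extra analysis. No new data, visits or patients are needed.
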